3.2. Discussion of Design

Results are interpreted according to working criteria which are based upon published works, as well as the clinical experience of TKL Research, Inc. These working criteria are periodically reviewed and amended subject to new information that becomes available.

This photoallergy study is designed to detect the ability of the CCP-020 (Diacerein 1%) topical ointment and vehicle ointment to cause photoallergic skin reactions when exposed to sunlight. Each subject is to receive applications of the CCP-020 (Diacerein 1%) topical ointment and the vehicle ointment product to 2 separate sites. One will be irradiated and one will remain non-irradiated. An untreated non-occluded control site will also be irradiated at Challenge. This design provides built-in controls for the test product CCP-020 (Diacerein 1%) topical ointment under both irradiated and non-irradiated conditions.

3.3. Study Population

3.3.1. Subject Population

A sufficient number of subjects will be enrolled in order to provide 50 completed subjects evaluable for analysis; an individual subject will be allowed to participate in the study one time only.

A rationale for the choice of sample size is provided in [Section 4.2](#) of this protocol.

3.3.2. Inclusion and Exclusion Criteria

Inclusion Criteria

A subject will be considered eligible for participation in the study if all of the following inclusion criteria are satisfied prior to randomization:

1. Is a healthy male or female (to be confirmed by medical history);
2. Is 18 years of age or older;
3. In the case of a female of childbearing potential, is using an acceptable form of birth control (oral/implant/injectable/transdermal contraceptives, intrauterine device, condom with spermicide, diaphragm with spermicide, abstinence, partner's vasectomy, tubal ligation). Abstinence or vasectomies are acceptable if the female subject agrees to implement one of the other acceptable methods of birth control if her lifestyle/partner changes;
4. In the case of a female of childbearing potential, has a negative urine pregnancy test (UPT) at Day 1 and are willing to submit to a UPT at the end of study (EOS);
5. Is free of any systemic or dermatological disorder, which, in the opinion of the Investigator, will interfere with the study results or increase the risk of AEs;

6. Has uniformly-colored skin on the lower thoracic area of the back which will allow discernment of erythema, and has Fitzpatrick Skin Types I, II, or III (see [Table 1](#));
7. Complete a medical screening procedure; and
8. Read, understand, and sign an informed consent.

Exclusion criteria

A subject who has any of the following will be excluded from the study:

1. Has a history of photosensitivity or photoallergy;
2. Has any visible skin disease at the application site which, in the opinion of the Investigator, will interfere with the evaluation of the test site reaction;
3. Is using systemic/topical corticosteroids within 3 weeks prior to and/or during the study, or systemic/topical antihistamines 72 hours prior to and during the study;
4. Is not willing to refrain from using systemic/topical anti-inflammatory analgesics such as aspirin (81 mg daily aspirin will be allowed), Aleve, Motrin, Advil, or Nuprin for 72 hours prior to and during the study (occasional use of acetaminophen will be permitted);
5. Are taking medication known to cause phototoxic reactions (eg, tetracyclines, thiazides, nonsteroidal anti-inflammatory drugs [NSAIDS]);
6. Is using medication which, in the opinion of the Investigator, will interfere with the study results (e.g. anti-inflammatory medications, antipsychotics, anticonvulsants with potential pain relief effects, immunomodulatory medications, and others);
7. Is unwilling or unable to refrain from the use of sunscreens, cosmetics, creams, ointments, lotions or similar products on the back during the study;
8. Has psoriasis and/or active atopic dermatitis/eczema;
9. Has a known sensitivity or allergy to constituents of the materials being evaluated including diacetin, mineral oil, petrolatum, cetyl alcohol, D&C Yellow #10 and/or ethyl paraben;
10. Is a female who is pregnant, plans to become pregnant during the study, or is breast feeding a child;
11. Has damaged skin in or around the test sites, including sunburn, excessively deep tans, uneven skin tones, tattoos, scars, excessive hair, numerous freckles, or other disfigurements of the test site;
12. Has received treatment for any type of internal cancer within 5 years prior to study entry;
13. Has a history of, or are currently being treated for skin cancer and/or hepatitis;
14. Has a history of, or is currently being treated for diabetes;
15. Has any condition that might compromise study results;
16. Currently or expect to sunbathe or use tanning salons during the study;

17. Has a history of adverse response (eg, blistering, sun poisoning) to ultraviolet (UV) sun lamps/sunlight exposure;
18. Is currently participating in any clinical testing;
19. Has any known sensitivity to adhesives; and/or
20. Has received any investigational drug(s) within 4 weeks prior to study entry.

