1.1. Background Information

CCP-020 (previously developed as AC-203) is a topical ointment containing diacerein (4,5-bis[acetoxy]-9,10-dihydro-9,10-dioxo-2-anthracene carboxylic acid; also known as diacetyl-rhein), a highly purified anthraquinone derivative, and is being developed by Castle Creek Pharmaceuticals for the treatment of epidermolysis bullosa simplex (EBS). The capsule formulation of diacerein, intended for oral use and systemic absorption, was initially approved for use in osteoarthritis (OA) in France in 1992 (as Artodar[®], ART50[®], or Zondar[®]). Since then, it has received marketing authorization in over 30 countries in Europe, South America, and Asia. It is classified as a Symptomatic Slow-Acting Drug in OA. Following oral administration of the capsule formulation, diacerein is rapidly metabolized to the deacetylated active metabolite, rhein. Similarly, diacerein in the topical formulation is hydrolyzed to rhein in the epidermis and the dermis following administration. Diacerein and rhein have been shown to inhibit the in vitro and in vivo production and activity of interleukin (IL)-1 β and other proinflammatory cytokines. It has a novel mode of action that differentiates it from non-steroidal anti-inflammatory drugs (NSAIDs) and other conventional forms of drug therapy.

For the development of CCP-020, a total of 10 animal studies have been conducted with CCP-020 ointment 1%, including one skin penetration study, three acute dermal toxicity studies, one phototoxicity study, three pharmacokinetic studies, and two sub-chronic juvenile toxicity studies. CCP-020 was well-tolerated in these studies and no untoward adverse effects (AEs) were noted. To date, two clinical studies of CCP-020 have been completed in patients with epidermolysis bullosa simplex (EBS). These include a Phase one pilot study in five patients and a Phase 2, multiple-site study in 17 patients in Europe. The Phase 2 study demonstrated CCP-020 was well-tolerated and no treatment-related AEs were reported. The Investigator's Brochure should be consulted for summaries of the results of these studies.¹

This Phase 1 study will assess the photoallergic potential of CCP-020 (Diacerein 1%) topical ointment.

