3.3.3. Interruption or Discontinuation of Treatment

A reaction of at least moderate erythema (2) accompanied with mild, but definite edema (1) to a study product observed after the first patch application/irradiation sequences of the Induction Phase may indicate the subject to be pre-sensitized, and may cause the discontinuation of the subject from the study.

After the second reading of the Induction Phase, either of the following conditions will require the study product be applied to a naive patch site under semi-occlusive patch conditions:

- Reaction of >50% “p” or “p” with no erythema, minimal/doubtful erythema, or definite erythema; or “D” (see [Tables 3 and 4](#));
- Any reaction of definite erythema with definite edema.

Study product may not be relocated more than twice.

The 3 weeks of continuous patch contact during the Induction Phase frequently results in tape-related irritation that is exacerbated by warm weather, but which occurs among some individuals irrespective of the season. Tape-related irritation will not be graded as a photosensitivity response at the patch site, but will be noted separately on the CRF. Severe tape-related irritation will necessitate a change in the application site. As above, the application site will only be changed twice and then the subject must be discontinued.

One application/irradiation session may be missed during the Induction Phase. It must be made-up during Week 4. In this case, no evaluation will be required following irradiation. Only one missed patch application for study product is allowed. A subject must be discontinued and considered not complete if more than one application is missed.

In accordance with legal requirements and ICH-GCP guidelines, every subject or his/her legal representative has the right to refuse further participation in the study at any time and without providing reasons (see also [Section 5.3](#)). A subject's participation is to be terminated immediately upon his/her request. The Investigator should seek to obtain the reason and record this on the case report form (CRF).

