3.4.6. Prior and Concomitant Therapy

All medications, including over the counter (OTC) drugs and vitamins, taken within 28 days prior to the start of the study will be recorded at Screening. Thereafter, a record of all medications taken during the course of the study will be made. Information regarding the total daily dose, route of administration, start and discontinuation dates, and indication are to be captured on the subject's CRF.

The following prohibitions will apply for the duration of the study:

- There will be no use of systemic/topical anti-inflammatory analgesics which in the opinion of the investigative personnel will interfere with the study results, including anti-inflammatory medications such as aspirin (81 mg aspirin will be allowed at the discretion of the Investigator), Aleve, Motrin, Advil, or Nuprin for 72 hours prior to and during the study (occasional use of acetaminophen will be permitted);
- Use of sunbeds or sunlamps or deliberate exposure of the test sites to natural sunlight or to other sources of UV light;
- Participation in any other clinical study;
- Soaking of test areas; and/or
- Application of any product to the test areas.

The use of or change in the dose of any and all concomitant medication, either prescription or OTC, during the study will be recorded. The reason for use or change of dose of a concomitant therapy may need to be reported as an AE. Therapies (medication and non-medication therapies)

not restricted by the protocol may be used. Non-prohibited chronic therapies being used at Baseline may be continued.

All topical or systemic medication listed in the exclusion criteria are prohibited during this study. See the IB for information about possible drug-drug interactions.¹

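### Exclusion 9 names 'diacetin' rather than the active ingredient diacerein, and no criterion addresses earlier exposure to diacerein or CCP-020 (minor)

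*Combined protocol and SAP*

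**What the plan says.** **Allergy.** Exclusion 9 in section 3.3.2 bars a subject with a known sensitivity or allergy to "constituents of the materials being evaluated including diacetin, mineral oil, petrolatum, cetyl alcohol, D&C Yellow #10 and/or ethyl paraben". Section 1.1 says that CCP-020 "is a topical ointment containing diacerein". It gives one synonym for the active, "also known as diacetyl-rhein", and says that the drug is converted to rhein in the skin. Neither diacerein, diacetyl-rhein nor rhein is in the exclusion 9 list.

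**Earlier exposure.** Four provisions bear on it:
- Exclusion 20 reads: "Has received any investigational drug(s) within 4 weeks prior to study entry".
- Section 3.4.6 requires that medications "taken within 28 days prior to the start of the study will be recorded at Screening".
- Section 3.3.1 states that "an individual subject will be allowed to participate in the study one time only".
- Section 3.3.3 says that moderate erythema with mild edema after the first application and irradiation "may indicate the subject to be pre-sensitized, and may cause the discontinuation of the subject from the study".

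On where earlier exposure could come from, section 1.1 says of oral diacerein that "it has received marketing authorization in over 30 countries in Europe, South America, and Asia". It also reports two completed CCP-020 studies in epidermolysis bullosa simplex (EBS), with 5 and 17 patients.

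**The concern.** The study asks whether repeated application plus irradiation induces photoallergy, using Induction, Rest and then Challenge on naive sites. That question presumes subjects who are not already sensitized. Two features of the eligibility text serve that presumption poorly.

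First, the list that a screener would most naturally read aloud contains a compound the protocol never defines and omits the one under test. A volunteer who has reacted to diacerein may not connect that history with the names being read.

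Second, someone who took diacerein or used CCP-020 more than four weeks ago, and has no recognized allergy, meets every criterion. If that person were already photosensitized, a reaction at Challenge would not have been induced by this regimen. Section 4.6.2 counts photosensitization reactions by treatment and gives no rule for separating induced from pre-existing ones.

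**Working it through.** The plan has no figure of its own on this point. The 50 evaluable subjects in section 4.2 rest on convention, without an assumed rate or power, so there is nothing to reproduce. The check is a comparison of texts, followed by an illustration of scale.

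**Step 1: is the active named?** Exclusion 9 lists six substances: 'diacetin', mineral oil, petrolatum, cetyl alcohol, D&C Yellow #10 and ethyl paraben. None matches diacerein or the synonym in section 1.1. Sections 3.4.1 and 3.4.2 describe the product without an ingredient list, so the protocol alone cannot show whether diacetin is an excipient or a slip. In either case the active is absent from the list.

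**Step 2: is a diacerein allergy excluded all the same?** Yes. The criterion covers constituents of the test materials, and the list only gives examples. The product name carries the word diacerein.

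**Step 3: what catches earlier exposure?**

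| Provision | Reach | What it leaves open |
|---|---|---|
| Exclusion 20 | Investigational drugs, 4 weeks (4 × 7 = 28 days) | CCP-020/AC-203 before that; marketed oral diacerein at any time |
| Section 3.4.6 record | All medications, 28 days | Anything older |
| Section 3.3.1 | This study only | Other studies |
| Exclusions 1, 15 and 17 | Known photosensitivity; conditions that might compromise results; known adverse UV response | Sensitization that nobody has recognized |
| Section 3.3.3 | A strong early reaction | Weaker reactions; acts after patching and irradiation; discretionary |

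Exposure more than 28 days before entry, with no recognized allergy, passes every line at entry.

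**Step 4: how many people could this be?** Documented completed CCP-020 exposure is 5 + 17 = 22 patients, all with EBS. The documents give no prevalence of earlier diacerein sensitization among healthy volunteers. For an assumed prevalence *p*, the chance of at least one such entrant among 50 is 1 − (1 − *p*)^50:

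| Assumed *p* | Chance of at least one |
|---|---|
| 0.01% | 0.5% |
| 0.1% | 4.9% |
| 1% | 39.5% |

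These chances bound the problem from above, because an entrant must also escape the safeguards in Step 3 and be scored as induced. Nothing in the documents points to the high end.

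**Step 5: what would one misattributed positive do?** Exact (Clopper-Pearson) 95% intervals with n = 50:
- 0/50: the upper limit is 1 − 0.025^(1/50) = 0.0711, giving 0 to 7.1%.
- 1/50: the lower limit is 1 − 0.975^(1/50) = 0.0005. The upper limit is the 97.5% point of Beta(2, 49), 0.1065. The result is 2.0%, with interval 0.05 to 10.6%.

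The upper limit rises by about 3.5 percentage points (10.65 − 7.11 = 3.54). Section 4.6.2 calculates an interval only if photosensitization occurs, so the 0/50 interval is an illustration and not a planned output.

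**The case against.** The strongest reply is that nothing of substance is missing. Exclusion 9 already covers every constituent, the product is called Diacerein 1% ointment throughout, and no screening form is available to show that staff would ask only about the listed names. This stands. A reader might infer that a person with known diacerein allergy is eligible; the criterion's wording does not support that.

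It can also be said that 'diacetin' may be a fault of PDF reading. That cannot be ruled out from one occurrence, although diacerein reads correctly elsewhere. It is a reason to check the source page first.

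On earlier exposure, a reader might infer that exclusion 20 readmits former CCP-020 trial patients after four weeks. The documented pool makes this empty in practice. Those 22 patients have EBS and would hardly qualify as healthy subjects free of an interfering skin disorder (inclusions 1 and 5). Oral diacerein is described as authorized in Europe, South America and Asia, for osteoarthritis, and no US authorization is mentioned for this single-center study. Exposure is also not sensitization: the Phase 2 study reported no treatment-related AEs. These points stand and keep the expected number near zero.

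Finally, section 3.3.3 foresees pre-sensitized subjects, and section 3.3.1 enrolls until 50 are complete, so a subject discontinued early costs no sample size. The non-irradiated sites and the Rechallenge rule in section 3.5.7.1 also help to separate contact allergy from photoallergy. All of this stands, but the section 3.3.3 check needs a reaction of some strength, is optional, and comes only after exposure. A direct question before entry would do what it cannot.

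The protocol nowhere states that subjects must be diacerein-naive. That requirement is inferred from the aim of testing induction.

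**Conclusion.** Minor, in two parts. The firmer part is that exclusion 9 does not name the active and does name an undefined compound. If the source page agrees with the text as read, that is a wording error in a subject-protection criterion. The second part is that earlier diacerein or CCP-020/AC-203 exposure is neither barred nor asked about beyond 28 days.

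The likely number of subjects affected is zero or very small. This is a judgment from the documented exposure, not an estimate. The 0/50 to 1/50 shift is conditional on one misattributed positive and says nothing about how likely that is. A reader might go on to infer that the photosensitization result is biased or that 50 subjects is the wrong number. Neither follows: the sample size and the analysis are unaffected. The point rests on the assumption that the study is meant to measure reactions induced by its own regimen, as its title and design indicate.

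**What to change.** 1. Check exclusion 9 against the source page, then reconcile it with section 1.1 so that diacerein is named. Keep diacetin only if it is truly an ingredient.
2. Add an exclusion for known previous exposure to diacerein by any route, or to CCP-020/AC-203.
3. Ask about it directly at Screening, with no time limit. The planned medication record cannot supply the answer because it looks back only 28 days, and the medical history includes no question on past diacerein use.

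The cost is a word or two in one criterion, one added line, and one extra Screening question. The effect on recruitment of healthy volunteers should be negligible.

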3.3.3. Interruption or Discontinuation of Treatment

A reaction of at least moderate erythema (2) accompanied with mild, but definite edema (1) to a study product observed after the first patch application/irradiation sequences of the Induction Phase may indicate the subject to be pre-sensitized, and may cause the discontinuation of the subject from the study.

After the second reading of the Induction Phase, either of the following conditions will require the study product be applied to a naive patch site under semi-occlusive patch conditions:

- Reaction of >50% “p” or “p” with no erythema, minimal/doubtful erythema, or definite erythema; or “D” (see [Tables 3 and 4](#));
- Any reaction of definite erythema with definite edema.

Study product may not be relocated more than twice.

The 3 weeks of continuous patch contact during the Induction Phase frequently results in tape-related irritation that is exacerbated by warm weather, but which occurs among some individuals irrespective of the season. Tape-related irritation will not be graded as a photosensitivity response at the patch site, but will be noted separately on the CRF. Severe tape-related irritation will necessitate a change in the application site. As above, the application site will only be changed twice and then the subject must be discontinued.

One application/irradiation session may be missed during the Induction Phase. It must be made-up during Week 4. In this case, no evaluation will be required following irradiation. Only one missed patch application for study product is allowed. A subject must be discontinued and considered not complete if more than one application is missed.

In accordance with legal requirements and ICH-GCP guidelines, every subject or his/her legal representative has the right to refuse further participation in the study at any time and without providing reasons (see also [Section 5.3](#)). A subject's participation is to be terminated immediately upon his/her request. The Investigator should seek to obtain the reason and record this on the case report form (CRF).

If at the time of refusal a study product has already been administered, the subject should be advised on follow-up safety investigations. If a subject withdraws from the study, all efforts will be made to complete a final evaluation if possible. Subjects discontinued for having experienced an AE will be followed until the AE is resolved, a reasonable explanation is provided for the event, or the subject is referred to his/her own primary medical doctor (PMD). The specific AE in question will be recorded on the appropriate CRF.

If a subject develops a serious adverse event (SAE), his/her termination from the study will be considered by the Investigator. Similarly, if the subject develops conditions over the course of

the study which would have excluded his/her entry in the study according to the safety-related medical exclusion criteria, he/she must be withdrawn immediately.

The subject may be withdrawn from the study at any time at the discretion of the Investigator for medical reasons and/or due to non-adherence to the treatment scheme and other duties stipulated in the study protocol. The reasons are to be documented on the CRF.

In addition, the Sponsor retains the right to end the study at any time if the study cannot be carried out as agreed upon in the protocol. In case of premature termination or suspension of the study, the Sponsor's study manager will promptly inform the Investigator/institutions and regulatory authorities of the termination or suspension and the reason for that. It is the responsibility of the Principal Investigator (PI) to notify the Institutional Review Board (IRB) in the case of premature termination/suspension.

3.3.4. Withdrawals

The following medical and other reasons justify a premature termination (by subject or Investigator) of any of the study IPs.

- Adverse Event/Serious Adverse Event
- Death
- Protocol Violation (e.g. non-compliance)
- Investigator Judgment
- Pregnancy
- Lost to Follow-up
- Withdrawal by Subject
- Study Terminated by Sponsor
- Other

If a subject withdraws from the study, all efforts will be made to complete a final evaluation, if possible. Subjects discontinued for having experienced an AE will be followed until the AE is resolved, a reasonable explanation is provided for the event, or the subject is referred to his/her own primary medical doctor (PMD). The specific AE in question will be recorded on the appropriate CRF.

